7.11.2 EXPECTED AE RELATED TO THE IVT INJECTION PROCEDURE

Mild discomfort related to the injection procedure (including use of an eyelid speculum, anaesthetic drops, mydriatic drops, antibiotic drops, povidone-iodine drops or flush and subconjunctival injection of anaesthetic, as well as the actual insertion of the IVT needle) are expected. These procedure-related adverse events include but are not limited to: redness, mild eye pain, eye irritation, visual disturbance, abnormal sensation in the eye, etc. and will be graded as indicated in Section 7.9.4.

7.11.3 DISEASE PROGRESSION

A condition considered by the PI as unequivocal AMD disease progression in the study eye or fellow eye should be identified as such in the participant's source documents and should not be recorded as an adverse event in the CRF, such as lesion growth, lesion bleeding, lesion that exudes fluid, an RPE tear, and extensive deposition of lipid. All other conditions should be recorded as an adverse event. The unequivocal nature of the disease progression must be indicated in the source documents. Normal progression or worsening of the medical condition under study (e.g. vision loss due to the progression of AMD), by itself, does not necessarily constitute an adverse event unless the change

can be reasonably attributed to an action of the test article and not only to its lack of efficacy.

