 - a. Women of non-childbearing potential (WONCBP), or
 - b. Women of childbearing potential (WOCBP) with a negative pregnancy test at screening and must agree to use protocol defined methods of contraception for the duration of the study.
 7. Males with female partners of childbearing potential must agree to use protocol defined methods of contraception and agree to refrain from donating sperm for the duration of the study.
 8. Willing and able to give informed consent.

Note: If both eyes meet the inclusion criteria, the eye with the best visual acuity at the screening visit will be designated as

the study eye. If both eyes have the same visual acuity, the right eye will be used as the study eye.

Exclusion Criteria: Unless specified otherwise, ocular specific exclusion criteria apply to the study eye only.

1. GA due to causes other than AMD such as Stargardt disease, cone rod dystrophy or toxic maculopathies like plaquenil maculopathy.
2. Spherical equivalent of the refractive error demonstrating > 6 dioptres of myopia or an axial length of >26 mm.
3. Evidence of exudative (wet) AMD including evidence of retinal pigment epithelium rips or evidence of neovascularization anywhere in the retina based on fluorescein angiogram as assessed by the PI in either eye within 12 months.
4. Retinal disease likely to confound visual performance or be affected by intraocular steroid.
5. Any ophthalmologic condition that reduces clarity of the media and that, in the opinion of the investigator interferes with ophthalmologic examination (e.g. advanced cataract or corneal abnormalities).
6. Any ophthalmologic condition that prevents adequate imaging of the retina judged by the PI.
7. Intraocular surgery (including lens replacement surgery) within 3 months prior to dosing.
8. Aphakia or absence of the posterior capsule. Previous violation of the posterior capsule is also excluded unless it occurred as a result of yttrium aluminum garnet (YAG) laser posterior capsulotomy in association with prior

posterior chamber intraocular lens implantation and at least 60 days prior to Day 0.

9. Any ophthalmologic condition that may require surgery during the study period.
10. Glaucoma or family history of glaucoma.
11. Any contraindication of IVT injection including current ocular or periocular infection.
12. History of uveitis or endophthalmitis.
13. History of choroidal neovascularization (CNV) in either eye.
14. History of IVT injection of steroids within 12 months.

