3.2 STUDY ENDPOINTS

3.2.1 PRIMARY SAFETY ENDPOINT

To demonstrate safety and tolerability of IVT injections of Fludrocortisone acetate based upon the mean change in GA lesion size as measured by Fundus Autofluorescence (FAF).

- Number and severity of local and systemic treatment emergent adverse events.
-

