6.2 SUBJECT ENROLLMENT

It is the responsibility of the investigator to ensure that subjects are eligible to participate in the study prior to enrollment and throughout the study. Documentation of the personally signed and dated informed consent of each subject, using the study-specific ICF, is required before initiating the Screening process. After written informed consent has been obtained and eligibility to participate established, investigative site personnel will obtain the subject's identification number. Only eligible subjects will be allocated to the open label FCA 1 mg/0.1mL or 2mg/0.1 mL.

Enrollment will occur in two parts in order to minimise the likelihood that subjects will be exposed to risks. During part 1 & 2, subjects will be screened one by one as only one patient will initially be enrolled during part 1 of the trial. The first enrolled subject will participate in a screening period of up to 14 days and a follow-up period of 28 days, to detect an IOP response.

After first subject has completed the follow-up of 28 days after FCA 1mg/0.1 mL injection, The subject's safety data will be reviewed the safety data of this will be reviewed by an independent safety review committee to determine whether to commence enrolment of additional 2 patients in the first cohort of 1mg/0.1mL dose of FCA. Enrolment will be stopped if >2 patients experience limiting-toxicity adverse event related to the study drug. If no more than two adverse events considered to be related to the study drug occur with limiting toxicity, the second cohort will be recruited. Dose-limiting toxicity is defined by intraocular inflammation, elevated IOP, reduced vision (loss of ≥ 15 letters), or haemorrhage within 28 days after injection.

Part 2 will take in place if the 3 subjects have tolerated well the dose. Part 2 initially involves a single subject treated with 2mg/0.1mL FCA to assess safety and tolerability. This subject will be followed for up to 28 days and reviewed by an independent safety

review committee prior to the recruitment of a further 5 subjects treated with 2mg/0.1mL FCA totalling in 6 subjects in the second cohort.

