7.10.4.2 CAUSALITY

The PI (or an authorized study physician) must submit an attribution for causality of the reported adverse event to the test article or procedure.

The attribution should take into account both the temporal association and any known physical, physiological or toxicological information regarding the test article that could reasonably infer causality. Causality should only be considered for the experimental test article and not for any standard study examination or diagnostic procedures. The four attribution categories are:

Unrelated	
Does not follow a reasonable temporal sequence from the administration of study drug.
 
The event or laboratory test abnormality is clearly due to extraneous causes (disease, other drugs, environment, etc.)

Unlikely related	
Does not follow a known pattern of response to study drug.
 
Does not follow a reasonable temporal sequence from the administration of study drug.
 
Disease or other drugs provides plausible explanation.
 
It does not reappear or worsen when study drug is re-administered

Possibly related	
Follows a known pattern of response to study drug.
 
Time sequence from administration of the study drug is reasonable.
 
Could also be explained by disease or other drugs.

Probably related	
Follows a known pattern of response to study drug.
 
Time sequence from administration of the study drug is reasonable.
 
Response to withdrawal clinically reasonable.
 
Cannot be reasonably explained by the known characteristics of the participant's clinical state, environmental factors, or other therapies administered to the subject

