7.11 EXPECTED ADVERSE EVENTS

7.11.1 EXPECTED AE RELATED TO THE TEST ARTICLE

No ocular or systemic AE related to the investigational drug are expected at the doses proposed in this protocol.

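### Section 7.11.3 keeps bleeding, exudation and RPE tear out of the AE data when judged AMD progression, so the primary safety count can miss new events, some of them also dose-limiting toxicities

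*Protocol*

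**What the plan says.** The primary safety endpoint in Section 3.2.1 includes "Number and severity of local and systemic treatment emergent adverse events". It has no relatedness condition.

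Section 7.11.3 then takes some events out of the data that feed this endpoint. It applies to "A condition considered by the PI as unequivocal AMD disease progression in the study eye or fellow eye". Such a condition "should not be recorded as an adverse event in the CRF, such as lesion growth, lesion bleeding, lesion that exudes fluid, an RPE tear"; extensive lipid deposits complete the list. The investigator must document in source that the progression is unequivocal, and every other condition is to be recorded. For worsening of the underlying disease, including vision loss, the rule is softer: by itself it "does not necessarily constitute an adverse event unless the change" can reasonably be traced to the test article.

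Section 6.2 and the synopsis use the same toxicity definition: "Dose-limiting toxicity is defined by intraocular inflammation, elevated IOP, reduced vision (loss of ≥ 15 letters), or haemorrhage within 28 days after injection". Neither makes an exception for disease progression.

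On causality, Section 7.10.4.2 lists "Follows a known pattern of response to study drug" first under both the possibly related and the probably related categories, and lists its negation under unlikely related. Section 7.11.1 states: "No ocular or systemic AE related to the investigational drug are expected at the doses proposed in this protocol". Section 2.3.3 says that the drug has not been given by this route in humans.

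**The concern.** The study has nine participants, no control group and no masking. Its main product is a list of what happened after injection. A rule that lets the treating investigator keep certain ocular events off that list can only shorten it.

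The listed events are not ordinary enlargement of the atrophy that was enrolled. Exclusion 3 bars exudative AMD, RPE rips or neovascularisation in either eye within 12 months. Exclusion 13 bars "History of choroidal neovascularization (CNV) in either eye", with no time limit. Section 2.2 describes leakage of fluid, lipid and blood as features of exudative AMD and treats geographic atrophy as the other advanced form. In an enrolled eye, bleeding or exudation would be a new event after an intravitreal injection, which is what a safety count exists to show.

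A second, smaller issue concerns relatedness. Section 8.3 bases the safe-and-tolerable conclusion on severe AEs related to the drug, and the stopping rule in Section 6.2 counts related events. If an investigator reads the known-pattern item as a requirement, an unfamiliar toxicity could be left out of both counts.

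**Working it through.** The protocol gives no event rate, power or error rate for safety, so there is no figure to reproduce. The check sets the sections side by side.

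**1. Which events fall under conflicting rules**

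| Study-eye event, judged unequivocal progression | AE in the CRF (7.11.3) | Dose-limiting toxicity if within 28 days (1.1, 6.2) |
|---|---|---|
| Lesion bleeding | No | Yes, haemorrhage is unqualified |
| Loss of at least 15 letters | Not necessarily, unless attributable to the drug | Yes |
| Exudation, RPE tear, lipid | No | Not named |
| Growth of the atrophic area | No | Not named; measured by FAF as a secondary endpoint |

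The first two rows conflict directly. The third row is a gap: these events enter neither the AE data nor the toxicity definition. Section 7.11.3 also sits badly with Section 7.10.1, which defines an AE without regard to cause.

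**2. Whether other parts of the plan recover the events**

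- Events of special interest (7.10.3): vitreous haemorrhage qualifies only if it is worse than 2+ and has not resolved within 14 days. Exudation and RPE tear are not listed.
- DSMB criteria (9.7): these name a 15-letter loss, IOP change and inflammation, but not haemorrhage, exudation or RPE tear. The closing catch-all refers to reported adverse events, so it inherits the 7.11.3 filter.
- Scheduled examinations (1.2): BCVA, SD-OCT, FAF and dilated ophthalmoscopy are planned at every visit. Section 8.4 summarises BCVA, OCT and ophthalmoscopy findings, but as efficacy data. They do not enter the TEAE count.

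**3. Where relatedness enters**

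| Place | Relatedness condition |
|---|---|
| Primary endpoint (1.1, 3.2.1) | No |
| Stopping rule, synopsis | No |
| Stopping rule, 6.2 | Yes |
| Tolerability guidance, 6.2 and 8.3 | Yes |
| Safe-and-tolerable criterion, 8.3 | Yes |

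The two stopping rules share the threshold of more than 2 patients but count different events. Relatedness touches the primary endpoint only through the fallback Grade 1 wording for transient events in Section 7.10.4.1.1. That affects severity, not the count.

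**4. What one event is worth**

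1/3 = 33.3 percentage points at 1 mg; 1/6 = 16.7 points at 2 mg. These follow from the cohort sizes and do not estimate any misclassification.

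**5. Illustration with assumed inputs**

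Let p be the true chance that a participant has a qualifying event, and c the share of such events that survives both the progression and the relatedness rules. Neither is in the documents. With all 9 enrolled and q = p × c, the chance that more than 2 are counted is

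P(X ≥ 3) = 1 − (1−q)^9 − 9q(1−q)^8 − 36q²(1−q)^7.

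For p = 0.20 and c = 0.5, q = 0.10: 1 − 0.387 − 0.387 − 0.172 = 0.053 after rounding.

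| Assumed p | c = 1 | c = 0.75 | c = 0.5 | c = 0.25 |
|---|---|---|---|---|
| 0.10 | 0.053 | 0.025 | 0.008 | 0.001 |
| 0.20 | 0.262 | 0.141 | 0.053 | 0.008 |
| 0.33 | 0.615 | 0.392 | 0.174 | 0.032 |
| 0.50 | 0.910 | 0.718 | 0.399 | 0.092 |

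The chance of counting none in the first 3 is (1−q)³. Going from c = 1 to c = 0.5, it rises from 0.512 to 0.729 at p = 0.20, and from 0.301 to 0.582 at p = 0.33.

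Section 7.11.3 cannot reach inflammation or raised IOP, so low values of c would need the relatedness rule to remove many events as well.

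**The case against.** The strongest defence is that the carve-out is bounded. Progression must be unequivocal, the judgement must be documented, and everything else is an AE. Vision loss stays an AE when it can be attributed to the drug. All of this stands. A reader might infer that the protocol removes vision loss from the safety data outright; it does not.

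A reader might also infer that the known-pattern item biases the primary endpoint, or that a novel toxicity must be classed as unlikely related. The documents support neither. The primary count includes all TEAEs, and Section 8.3 already plans summaries of all AEs, with relationship as a further breakdown. Section 7.10.4.2 does not say that every item in a category must be met, and it tells the investigator to weigh timing and toxicological knowledge. Some pattern is also known: Section 2.2 names cataract progression, ocular hypertension and endophthalmitis for intravitreal steroids, and Section 2.3.1 reports haemorrhage in rabbit eyes at 4 mg. What remains is an ambiguity: how many items are needed is not stated, and the protocol itself expects no drug-related event.

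Excluding earlier neovascular disease makes such events new; it does not prove that they cannot be AMD progression. That is correct. But without a control group the investigator has little basis for separating spontaneous conversion from an effect of the drug or injection, and no independent adjudication is stated.

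Finally, the events remain visible in the examination data and partly in DSMB review. This limits the damage, but does not put them back into the endpoint.

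**Conclusion.** The point holds in this form. Followed as written, Section 7.11.3 allows new study-eye bleeding, exudation, RPE tear or lipid deposition, and conditionally vision loss, to be left out of the primary TEAE count on the judgement of the unmasked investigator. For bleeding and a loss of at least 15 letters within 28 days, this contradicts a toxicity definition that has no such exception.

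The direction is fixed, because omitted events can only lower the count. The size is not known: the documents give neither an event rate nor a misclassification rate, and the probabilities above rest entirely on assumed values. It would be wrong to say that bias has been demonstrated.

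The relatedness issue is secondary. It can lower the counts behind the Section 8.3 conclusion and the Section 6.2 stopping rule, but not the primary TEAE count. The synopsis stopping rule has no relatedness condition, so the two versions disagree.

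**What to change.** - **Section 7.11.3 and CRF:** record every study-eye haemorrhage, exudation or neovascularisation, RPE tear and loss of at least 15 letters as an AE, with a flag for consistency with AMD progression. Limit the exemption to growth of the atrophic area, which FAF already measures.
- **Section 8.3:** tabulate TEAEs with and without flagged events, and show all-cause study-eye counts beside the related counts.
- **Section 7.10.4.2:** state that a known pattern of response is not required for the possibly related category.
- **Sections 1.1, 6.2 and 7.11.3:** reconcile the progression exemption with the dose-limiting toxicity definition, and the synopsis stopping rule with the one in Section 6.2. Which rule should apply is for the sponsor, the investigator and the DSMB to settle; this review does not propose one.

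The cost is amended protocol and CRF wording, a few more AE records and a slightly higher AE count. An event never entered as an AE cannot be reliably restored at analysis, so the recording change matters most.

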7.11.3.1 WITHDRAWAL

Participants may choose to withdraw from this study for any reason at any time without penalty or prohibition from enrolling in other clinical protocols.

Participant wishing to withdraw from the study completely will be offered an early termination visit.

This early termination visit will include the examinations outlined in Section 6.3.1.

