6.3.1 SCREENING – WITHIN 14 DAYS PRIOR TO TREATMENT

Visit 1 – All Subjects

All ophthalmic procedures (including imaging) are to be performed on both eyes:

1. Before any study specific procedures are performed, explain the purpose and nature of the study, and have the patient read, sign, and date the Institutional

Review Board/Independent Ethics Committee (IRB/IEC) - approved Informed Consent Form (ICF). Have the individual obtaining consent from the patient and a witness, if applicable, sign and date the ICF.

2. Obtain a screening number for the subject.
3. Obtain information on demographics, medical/ocular history, and concomitant medications used 90 days prior to enrollment. Include vitamins, and all over-the-counter as well as prescription medications.
4. Screen the patient for inclusion/exclusion criteria.
5. Collect blood (including blood for HCG/FSH/LH, if applicable) and urine for laboratory analysis and forward the samples to the central laboratory.
6. Collect vital signs.
7. Perform BCVA.
8. Perform LL-BCVA.
9. Perform a complete ophthalmic exam including slit-lamp exam of the cornea, iris, anterior chamber, lens (LOCS III if any opacity on the lens noted) and aqueous reaction (cells and flare), dilated fundus exam of the vitreous and retina and IOP measurement.
10. Perform SD-OCT imaging for determination of eligibility by the PI.
11. Perform FAF imaging for determination of eligibility by the PI.
12. Perform NIFR imaging.
13. Perform DCFP for determination of eligibility by the PI.
14. Perform FA for determination of eligibility by the PI.

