6.3.3 Visit 3 (Day 1) – All Subjects. Post-initial treatment examination

Unless specified, all ophthalmic procedures (including imaging) are to be performed on the **study eye only**.

1. Obtain information on any changes in medical health and/or the use of concomitant medications.
2. Collect vital signs.
3. Perform BCVA.
4. Perform LL-BCVA.

5. Perform a complete ophthalmic exam including slit-lamp exam of the cornea, iris, anterior chamber, lens (LOCS III if any opacity on the lens noted) and aqueous reaction (cells and flare), dilated fundus exam of the vitreous and retina and IOP measurement.
6. Monitor for adverse events

6.3.4 Follow-up Visits – Day 7, 14, 28, 60, 90

Unless specified, all ophthalmic procedures (including imaging) are to be performed on the **study eye only**. The following procedures will be performed at all follow-up visits:

1. Obtain information on any changes in medical health and/or the use of concomitant medications.
2. Collect vital signs.
3. Collect blood for PK analysis (days 7, 28 and 90 only).
4. Perform a complete ophthalmic exam including slit-lamp exam of the cornea, iris, anterior chamber, lens (LOCS III if any opacity on the lens noted) and aqueous reaction (cells and flare), dilated fundus exam of the vitreous and retina and IOP measurement.
5. Monitor for adverse events

6.3.5 Termination Visit (or Early Termination) – Day 150

All ophthalmic procedures are to be performed on BOTH EYES.

1. Obtain information on any changes in medical health and/or the use of concomitant medications.
2. Collect blood and urine for laboratory analysis and forward the samples to the central laboratory.
3. Collect blood for PK analysis.
4. Collect vital signs.
5. Perform urine pregnancy test. -WOCBP only.
6. Perform BCVA.

7. Perform a complete ophthalmic exam including slit-lamp exam of the cornea, iris, anterior chamber, lens (LOCS III if any opacity on the lens noted) and aqueous reaction (cells and flare), dilated fundus exam of the vitreous and retina and IOP measurement.
7. Perform SD-OCT imaging.
8. Perform FAF imaging.
9. Perform NIFR imaging.
10. Perform DCFP.
11. Perform FA imaging.
12. Monitor for adverse events

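### Section 7.11.3.1 points the early termination visit to the screening list (6.3.1), contradicting Section 6.3.5; followed literally, an early leaver has no exit PK draw

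*Protocol*

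**What the plan says.** Section 7.11.3.1 (Withdrawal) offers an early termination visit to participants who leave the study completely, and fixes its content by reference: "This early termination visit will include the examinations outlined in Section 6.3.1".

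The section it cites is headed "6.3.1 SCREENING – WITHIN 14 DAYS PRIOR TO TREATMENT". Its 14 items include consent, a screening number, eligibility, laboratory samples, vital signs, BCVA, LL-BCVA, a complete ophthalmic examination and imaging. Its only medication item asks for "concomitant medications used 90 days prior to enrollment". Its blood item reads "Collect blood (including blood for HCG/FSH/LH, if applicable) and urine for laboratory analysis".

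A different section carries early termination in its own title: "6.3.5 Termination Visit (or Early Termination) – Day 150". That list includes "Obtain information on any changes in medical health and/or the use of concomitant medications", "Collect blood for PK analysis" and, as its last item, adverse-event monitoring.

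The Schedule of Activities (Section 1.2) has a screening column and a Day 150 column but no early-termination column, so it does not settle which list applies.

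**The concern.** The withdrawal section is where a site would look when a participant leaves, and it sends the site to a pre-treatment visit. A screening list is not built to capture what happened after dosing. The study is small (9 planned participants in the Synopsis), and Section 2.3.3 states that the drug has not previously been given intravitreally in humans, so the last contact with each participant carries weight.

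The item most exposed is the PK sample. Section 3.2.2 lists exposure, maximum concentration, its time and terminal half-life. For someone who leaves between scheduled draws, the exit visit is the only remaining chance to extend the concentration profile.

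**Working it through.** No figure in the plan needs reproducing. The check sets the two lists side by side and then asks, for each difference, whether another section fills the gap.

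**Comparison of the lists**

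| Item | 6.3.1 (cited by 7.11.3.1) | 6.3.5 (titled early termination) | Rule elsewhere that covers it |
|---|---|---|---|
| PK blood | absent | listed | none found |
| Adverse-event monitoring | absent | listed | 7.10.4: AEs are probed at each subject visit |
| Health and medication changes since dosing | absent (pre-enrolment history only) | listed | 5.3: medications given at any time during the study are recorded; new health problems fall under AE probing |
| Pregnancy test | blood HCG where applicable | urine test, WOCBP | both lists test; the method differs |
| Laboratory blood and urine, vital signs, BCVA, ophthalmic examination with IOP, SD-OCT, FAF, NIFR, colour photography, FA | listed | listed | not needed |
| LL-BCVA | listed | absent | 7.5 treats it as part of BCVA testing |

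The Schedule agrees on the first two rows: its screening column has neither PK sampling nor adverse-event review, and its Day 150 column has both.

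**Size of the PK loss per leaver**

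Inputs: the Schedule marks PK on Days 0, 7, 28 and 150, which is four time points and matches the count in the Section 7.9 blood-volume table. Section 6.3.4 instead lists Days 7, 28 and 90 for follow-up. Assume that every scheduled sample before withdrawal was taken and that the participant accepts the exit visit. Samples with the exit draw = scheduled samples already taken + 1.

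| Time of withdrawal | Without exit draw | With exit draw | Share lost |
|---|---|---|---|
| After Day 0, before Day 7 | 1 | 2 | 1/2 |
| After Day 7, before Day 28 | 2 | 3 | 1/3 |
| After Day 28, before Day 150 (Schedule) | 3 | 4 | 1/4 |
| After Day 28, before Day 90 (with the 6.3.4 draw) | 3 | 4 | 1/4 |
| After Day 90, before Day 150 (with the 6.3.4 draw) | 4 | 5 | 1/5 |

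The missing sample is always the latest one, which bears most directly on terminal half-life.

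**Effect of correcting the reference alone**

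Replacing 6.3.1 by 6.3.5 restores the PK, adverse-event and medication items but removes the explicit LL-BCVA item. Change in LL-BCVA is a secondary endpoint in Section 3.2.2, so 6.3.5 should name it.

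**The case against.** The strongest reply is that this is a numbering slip with little practical effect. Other references are also stale: several parts of Sections 7.10 and 7.11 cite 7.9.x for text now at 7.10.x, and Section 2.3.3 cites 9.9 for the blood volumes now in 7.9. A careful site would find early termination in the heading of 6.3.5. Section 7.11.3.1 also imports only the examinations of 6.3.1, so nobody need repeat consent or eligibility, and most examinations coincide. This stands as a limit on the impact. It does not remove the contradiction, because both sections are operative text.

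A reader might infer more: that late adverse events and the drugs started for them go unrecorded, so that the primary endpoint is biased by selective loss among those who leave. The documents do not support this. Section 7.10.4 requires AE probing at each visit, Section 7.10 requires all AEs to be documented, and Section 5.3 requires medications given during the study to be recorded. Section 7.10.5 follows SAEs to resolution even after discontinuation, and Section 7.10.3 does the same for events of special interest among study subjects. Nor does the protocol say that early leavers are more likely to have had a problem.

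A reader might also count the pregnancy test as lost, but blood HCG is in 6.3.1 where applicable. Finally, one leaver is 1 of 9 participants, 1 of 3 at 1 mg or 1 of 6 at 2 mg. Those are the shares that one person represents, not an estimate of lost data.

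**Conclusion.** The contradiction is real and should be corrected. Sections 7.11.3.1 and 6.3.5 define the same visit differently, and the cited list belongs to a visit before treatment.

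The one consequence without a back-up rule is the exit PK sample: one sample per early leaver, or between 1/5 and 1/2 of that participant's profile depending on when they leave. This assumes that the site follows 7.11.3.1 literally, that earlier samples were taken and that the participant accepts the visit. The protocol states no dropout rate, so a study-level loss cannot be given.

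The adverse-event and medication items are missing from the cited list but required elsewhere, so the effect there is a weaker prompt at the exit visit, not an established loss. GA area and BCVA are unaffected because FAF and BCVA are in both lists. The point therefore does not rest on damage to the primary safety endpoint.

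**What to change.** In Section 7.11.3.1, replace the reference to Section 6.3.1 with Section 6.3.5. In Section 6.3.5, name LL-BCVA alongside BCVA. Section 7.5 already includes LL-BCVA in BCVA testing, so this makes an existing expectation explicit, although it adds a line to the 6.3.5 list.

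An early-termination column in the Schedule of Activities would help but is optional. If added, base it on the existing Day 150 column and reconcile that with 6.3.5. Copying 6.3.5 alone would omit the physical examination, VFQ-25, and height and weight, all of which the Schedule marks at the final visit, and would create a new mismatch.

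The cost is one corrected cross-reference and one added item, plus the Schedule column if wanted. The PK draw is already in 6.3.5, so no new sample type or visit is introduced.
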